- 4 All subjects who discontinue study treatment without experiencing any 1 of the following: death, disease relapse, treatment failure, or withdrawal of consent, will be followed every Day 1 (± 7 days) of Weeks 9, 17, 25, 33, 41, 53, and every 24 weeks thereafter for EFS until they experience treatment failure, relapse, death, withdraw from the study, or until the time when 173 EFS events have occurred or as deemed necessary by the IDMC.
- 5 Screening bone marrow aspirate (or peripheral blood sample if bone marrow aspirate is not available, with Medical Monitor approval) will be collected for central confirmation of IDH1-mutated disease prior to randomization, and can be conducted before the 28-day Screening window.
- 6 A buccal swab for germ-line mutation analysis will be obtained at Screening.
[REDACTED]
- 8 Subjects should start study treatment (ie, C1D1 [Week 1]) within 3 days (72 hours) of randomization.
- 9 Prior to first dose of study treatment, only AEs that are classified as SAEs deemed related to study procedures should be reported. After initiation of study drug, all AEs and SAEs, regardless of attribution, will be collected. Subjects will be assessed at the Follow-up Visit (4 weeks post-treatment) to determine if any new AEs have occurred. After this period, Investigators should report only SAEs that are considered to be related to study treatment (AG-120/placebo or azacitidine).
- 10 Height at Screening only. Weight and body surface area calculation should be conducted on Day 1 of each cycle, prior to dosing.
- 11 Vital signs (temperature, BP [sitting for 5 minutes], pulse rate, respiratory rate) are to be taken at Screening and at any point when abnormal vital signs are suspected. All clinically relevant abnormal vital sign results will be reported as AEs.

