- 14 Evaluation of disease status, including evaluation of bone marrow and/or peripheral blood, to be conducted: at Screening (or as part of Pre-screening as long as it is within 28 days prior to randomization); Day 1 (\pm 7 days) of Weeks 9, 17, 25, 33, 41, 53, and every 24 weeks thereafter; at EOT; during EFS follow-up on the same schedule; as clinically indicated; and/or any time that disease progression is suspected. Upon Sponsor unblinding, evaluation of disease status will no longer be collected. Subjects are expected to remain on treatment with AG-120/placebo as long as there are no unacceptable toxicities and the subject has a response of at least stable disease. Also includes assessment of transfusions (RBC and platelet), infections, length of any hospital stays, and other efficacy and safety measures that are potentially indicative of clinical benefit. De-identified copies of evaluation reports (bone marrow and/or peripheral blood assessment of disease status) should be submitted. Blood draws for regular hematology assessments (footnote 17) should be reviewed for the need to evaluate disease status at an unscheduled time point.
- 15 Clinically directed examinations, including a skin examination.
- 16 For female subjects with reproductive potential: A serum β -hCG pregnancy test is required at Screening and must be verified as negative within 72 hours prior to study treatment administration. A urine pregnancy test will be conducted on C1D1 and confirmed negative prior to dosing, and on Day 1 of all subsequent cycles. A urine pregnancy test should be conducted at the end of treatment visit.
- 17 Hematology: hemoglobin, RBC count, WBC count with differential, ANC, platelet count, and peripheral blast count. Hematology blood draws should occur prior to administration of any study drugs on visit date.
Chemistry: sodium, potassium, calcium, magnesium, albumin, glucose, BUN, creatinine, lactate dehydrogenase, ALP, AST, ALT, total bilirubin, phosphate, and bicarbonate. Chemistry blood draws should occur prior to administration of any study drugs on visit date.
Blood for hematology and chemistries is to be obtained: at Screening; on Days 1, 8, 15, and 22 (\pm 3 days) of Cycle 1 (Weeks 1, 2, 3, and 4); on Days 1 and 15 (\pm 3 days) of Cycles 2, 3, and 4 (Weeks 5, 7, 9, 11, 13, and 15); on Day 1 (\pm 3 days) of each treatment cycle thereafter (Weeks 17+); at EOT; and 4 weeks post-treatment.

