6.4.2. Standard Derivations and Reporting Conventions

The following conversion factors will be used to convert days into weeks, months or years: 1 week=7 days, 1 month=30.4375 days, and 1 year=365.25 days.

The following derivations will be implemented.

- Age (years):
 - $(\text{date of informed consent} - \text{date of birth} + 1) / 365.25$
 - If only day of birth is missing: Age (years): $(\text{year/month of informed consent} - \text{year/month of birth})$
 - If day and month of birth are missing: Age (years): $(\text{year of informed consent} - \text{year of birth})$

The integer part of the calculated age will be used for reporting purposes.

- $\text{BMI (kg/m}^2\text{)} = \text{weight (kg)/height (m)}^2$
- BSA (m^2) as collected in the eCRF
- Duration (in days) from a reference date (eg, randomization date, start date of study treatment)=
 - date of event–reference date+1, if the date of the event is on or after the reference date
 - date of event–reference date, if the date of the event is before the reference date

Reporting conventions will be as follows:

- Mean and median will be displayed to one more decimal place than the raw data
- Standard deviation (SD) will be displayed to two more decimal places than the raw data
- Percentages will be displayed to 1 decimal place (however, percentages corresponding to 0 counts will be reported as 0 rather than 0.0 and 100 percent will be reported as 100 rather than 100.0)
- p-values will be reported with 4 decimal places; all p-values should be specified to be 1-sided or 2-sided
- Unless otherwise specified, rounding will be performed to the closest integer/first decimal using the common mid-point between the two consecutive values, eg, 5.11 to 5.14 will be rounded to 5.1, and 5.15 to 5.19 will be rounded to 5.2
 - Non-zero percentages that are <0.1 before rounding will be displayed as “<0.1”, eg, 0.09 will be reported as <0.1 rather than as 0.1
 - p-values <0.0001 before rounding will be displayed as “<0.0001”, eg, a p-value of 0.00009 will be displayed as <0.0001 rather than as 0.0001

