7.7.1.1.1. Determination of Event or Censoring for EFS

Evaluation of disease status, including evaluation of bone marrow and/or peripheral blood, is planned to be conducted at Screening (or as part of Pre-screening if within 28 days prior to randomization); Day 1 (± 7 days) of Weeks 9, 17, 25, 33, 41, 53, and every 24 weeks thereafter; at End of Treatment (EOT); during EFS follow-up on the same schedule; as clinically indicated; and/or any time that disease progression is suspected.

Determination of relapse date

Only disease assessments performed before the start date of subsequent anticancer therapies will be considered in the determination of relapse.

Confirmation is required for relapse. Assessments which are not done or not evaluable are ignored in the derivation of relapse confirmation. A subject will be considered to have relapsed if either of the following criteria are met:

- Relapse in 2 consecutive assessments that are at least 4 weeks apart
- Relapse with no further evaluable disease assessments before discontinuation from study or initiation of subsequent anticancer therapy

The date of relapse considered in the analyses will be the date when the first relapse, that is subsequently confirmed, is observed.

Determination of CR by 24 weeks

CR will be assessed until the date of relapse (that is subsequently confirmed). Only assessments performed on or before the start date of subsequent anticancer therapies will be considered in the determination of CR.

The protocol allows a 1-week window for disease assessments. Therefore, a subject will be considered to have achieved “CR by 24 weeks” if the date of first CR is within 25 weeks (24 weeks target+1 week window) after the date of randomization:

CR by 24 weeks if date of first CR–date of randomization $\leq 24 \times 7 + 7$.

Determination of two or more missing assessments

In the primary analysis of EFS, if a subject has an EFS event (relapse or death) after two or more missing disease assessments, the subject will be censored at the last adequate disease assessment documenting no relapse before the missing assessments. The followings are the rules for determining whether two or more disease assessments are missed.

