- If the event date is prior to day 1 of week 53 (relative day since randomization $\leq 52 \times 7 = 364$), and the difference of event date and the last adequate disease assessment $> (8 \times 2 + 1) \times 7 = 119$, then the event is considered as occurring after two or more missing disease assessments
- If the event date is between day 1 of week 53 and day 1 of week 77 (relative day since randomization > 364 and ≤ 532) and the difference of event date and the last adequate disease assessment $> (8 + 12 + 1) \times 7 = 147$, then the event is considered as occurring after two or more missing disease assessments
- If the event date is between day 1 of week 77 and day 1 of week 101 (relative day since randomization > 532 and ≤ 700) and the difference event date and the last adequate disease assessment is $> (12 + 24 + 1) \times 7 = 259$, then the event is considered as occurring after two or more missing disease assessments
- If the event date is after day 1 of week 101 (relative day since randomization > 700) and the difference of event date and the last adequate disease assessment is

$>(24+24+1)\times 7=343$, then the event is considered as occurring after two or more missing disease assessments

The outcome (event or censor), type of event and the date of event or censoring to be considered for the primary analysis of EFS are presented in Table 5.

Table 5: Outcome and Event or Censoring Dates for EFS

Scenario	Date of event/censoring	Event (event type)/ Censored
CR by 24 weeks ^a then relapse	Date of relapse	Event (relapse)
CR by 24 weeks ^a then death (no relapse)	Date of death	Event (death)
CR by 24 weeks ^a then start subsequent anticancer therapy (prior to relapse or no relapse)	Date of the last adequate disease assessment documenting no relapse prior to start of subsequent anticancer therapy or missed response assessments	Censored
CR by 24 weeks ^a then relapse or death after two or more missing or inadequate disease assessments		Censored
CR by 24 weeks ^a and neither relapse nor death		Censored
On treatment ≥ 24 weeks without CR by 24 weeks ^a	Date of randomization	Event (TF, on treatment ≥ 24 weeks without CR)
Treatment discontinuation prior to 24 weeks, without CR by 24 weeks ^a		Event (TF, treatment discontinuation prior to 24 weeks without CR)

Abbreviations: CR = complete response; EFS = event-free survival; TF = treatment failure.

^a Based on the protocol schedule of assessments, "+1 week window" is allowed.

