Frequency of subject with each event type and censoring reasons will be presented by treatment arm. Reasons for censoring will be summarized according to the categories in Table 6 following the hierarchy shown.

Table 6: EFS Censoring Reasons and Hierarchy

Hierarchy	Condition	Censoring Reason
1	CR by 24 weeks then start subsequent anticancer therapy	CR by 24 weeks, start subsequent anticancer therapy
2	CR by 24 weeks then relapse or death after two or more missing or inadequate disease assessments	CR by 24 weeks, relapse/death documented after two or more missing disease assessments
4	CR by 24 weeks, no relapse or death, lost to follow-up	CR by 24 weeks, lost to follow-up
5	CR by 24 weeks, no relapse or death, withdrawal by subject from the study	CR by 24 weeks, withdrawal by subject
6	CR by 24 weeks, no relapse or death, ongoing in study	CR by 24 weeks, ongoing without relapse or death

Abbreviations: CR = complete response; EFS = event-free survival.

The EFS event or censoring time, event type and the reason for censoring will also be presented in a by-subject listing.

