7.7.1.2. Sensitivity Analyses for EFS

The following sensitivity analyses will be performed:

1. EFS will be tested using the log-rank test stratified by the IRT randomization stratification factors and based on the FAS. The time of relapse or death is determined using the actual date of relapse or death, even in situations where relapse or death is observed after two or more missing disease assessment or start of subsequent anticancer therapy.
2. EFS will be tested using the unstratified log-rank test and based on the FAS.
3. EFS will be tested using the log-rank test stratified by the IRT randomization stratification factors and based on the PPS.
4. EFS will be tested using the log-rank test stratified by the randomization stratification factors derived based on data provided by the Investigator in the eCRF and based on the FAS.
5. EFS will be tested using the log-rank test stratified by the IRT randomization stratification factors and based on the FAS. For the subjects who do not achieve CR by Week 24, instead of being considered to have had an EFS event at Day 1 of randomization, the event time will be either 24 weeks or EOT, whichever is earlier.

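### The missed-visit censoring rule for EFS picks its gap limit by event date while visit intervals widen, so some events are censored after one missed visit or none

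*SAP*

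**What the plan says.** SAP 7.7.1.1.1 states the purpose of the rule for the primary analysis: "if a subject has an EFS event (relapse or death) after two or more missing disease assessments, the subject will be censored", with censoring at the last adequate assessment that showed no relapse. Disease is assessed on Day 1 (±7 days) of "Weeks 9, 17, 25, 33, 41, 53, and every 24 weeks thereafter". Intervals are therefore 8 weeks up to Week 41, 12 weeks from Week 41 to Week 53, and 24 weeks after that.

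The rule is put into practice through the time from the last adequate assessment to the event. The limit depends on the event day counted from randomization:

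- up to day 364: more than 119 days
- days 365 to 532 ("If the event date is between day 1 of week 53 and day 1 of week 77"): more than 147 days
- days 533 to 700: more than 259 days
- after day 700: more than 343 days

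SAP Table 6 reports such subjects, by arm, under the reason "relapse/death documented after two or more missing disease assessments". Sensitivity analysis 1 in SAP 7.7.1.2 uses actual event dates, "even in situations where relapse or death is observed after two or more missing disease assessment or start of subsequent anticancer therapy". The protocol gives no day limits, so the SAP text is the only operational definition.

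**The concern.** Each limit is the sum of the two visit intervals that end at the visit opening the band, plus one week. It is then applied to every event in the band. Because intervals lengthen, a subject whose event falls late in a band may be in, or one visit beyond, an interval longer than those the limit was built from. The gap can then exceed the limit although fewer than two visits were missed.

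This happens in the primary test, which also gates every key secondary endpoint. The exposed subjects are the CR responders, whose EFS the protocol (12.5.1) presents as more meaningful than the overall hazard ratio. What is at stake is a borderline result, the responder EFS estimates, and a censoring table that records missed visits that did not occur.

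**Working it through.** **1. The SAP's limits reproduce.** Two intervals plus one week, in days:

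- (8 + 8 + 1) × 7 = 119
- (8 + 12 + 1) × 7 = 147
- (12 + 24 + 1) × 7 = 259
- (24 + 24 + 1) × 7 = 343

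The arithmetic is right; the question is which date selects the limit.

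**2. Day numbering.** SAP 6.4.2 adds one day to a duration "if the date of the event is on or after the reference date", so randomization is day 1. Day 1 of Week w is then 7(w − 1) + 1: W33 = 225, W41 = 281, W53 = 365, W77 = 533, W101 = 701.

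**3. Events censored after fewer than two missed visits, nominal visit days.**

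| Last adequate visit | Visits missed | Event days | Gap (days) | Limit applied |
|---|---|---|---|---|
| W53 (365) | none | 513–532 | 148–167 | 147 |
| W33 (225) | W41 | 345–364 | 120–139 | 119 |
| W41 (281) | W53 | 429–532 | 148–251 | 147 |
| W53 (365) | W77 | 625–700 | 260–335 | 259 |

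The no-miss row exists because W53 to W77 is 24 × 7 = 168 days and the limit is 147. On nominal dates no event with two closed visit windows escapes censoring, so the error is over-censoring only.

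**4. Dosing offset.** Protocol Table 6, footnote 8: "Subjects should start study treatment (ie, C1D1 [Week 1]) within 3 days (72 hours) of randomization". If weeks run from C1D1 and dosing starts 3 days after randomization, each range starts 3 days later: 516–532 (none missed), and 348–364, 432–532 and 628–700 (one missed). None disappears.

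**5. Relapse found at an attended W77 visit.** At offset 0, a W77 visit held 1 to 7 days early falls on days 526–532 and gets the 147-day limit. Even against a W53 visit held 7 days late (day 372) the gap is at least 526 − 372 = 154 days. So 7 × 15 = 105 of the 15 × 15 = 225 within-window timing pairs are flagged with full attendance. At offsets 1, 2 and 3 the counts are 6 × 15 = 90, 5 × 15 = 75 and 4 × 15 = 60. These are combinations, not probabilities.

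**6. Exposed events.** Under the design assumptions, responders number 100 × 20% + 100 × 40% = 60. The other 140 are treatment failures dated to randomization and cannot be affected. That leaves 173 − 140 = 33 responder events.

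**7. Wrongly censored events per trial.** The documents give no attendance, visit-timing or event-dating data, so these are assumptions. The simulation used the design inputs: 200 subjects 1:1; CR 40% vs 20%; exponential medians of 19.2 and 14.6 months; accrual of 3 then 5 per month; 5% dropout; cutoff at 173 events with at least 24 weeks of follow-up. Visits were missed independently, and a visit counted as missed only if its whole window closed before the event. There were 1,000 trials per scenario. Responder events averaged about 35 to 36, since the follow-up minimum can carry a trial past 173. With half of events dated at visits:

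| Visit timing; dosing offset (days) | 0% missed | 5% missed | 10% missed |
|---|---|---|---|
| nominal; 0 | 0.29 | 0.41 | 0.53 |
| 0–7 days late; 0 | 0.21 | 0.29 | 0.48 |
| ±3 days; 0–3 | 0.83 | 0.96 | 1.18 |
| ±7 days; 0–3 | 1.19 | 1.56 | 1.93 |
| ±7 days; 0 | 1.43 | 1.90 | 2.28 |

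If all events are dated continuously the range is 0.4 to 1.0. If all are dated at visits it is 0.0 to 3.4, an extreme because EFS includes deaths. If every visit were 0 to 7 days early, also an extreme, the half-and-half figure reaches 3.2 and the visit-dated figure 5.5.

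**8. Effect on the stratified log-rank test, SAP rule against visit counting.** Half-and-half dating, 4,000 trials each, with assumed non-prognostic strata shares (75/25 for AML status; 25/40/10/25 for region):

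| Scenario | Mean Z shift | Significance lost | Gained |
|---|---|---|---|
| nominal, 5% missed | 0.003 | 0.35% | 0.30% |
| ±7 days, offset 0–3, 5% missed | 0.007 | 0.80% | 1.03% |
| ±7 days, offset 0, 10% missed | 0.008 | 1.20% | 1.40% |

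Power changes by 0.2 points or less. The single-trial Z shift lies within −0.20 to +0.22 (5th to 95th percentile).

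**The case against.** The best case against acting is size. By these figures the mean effect on Z is negligible, no direction of bias appears, decision changes split about evenly, and some 140 of the 173 events are untouchable.

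The counts may also be too high. Protocol Table 6 says blood results "should be reviewed for the need to evaluate disease status at an unscheduled time point". Unscheduled no-relapse assessments at 0.5 to 2 per year lower one mid-range case (±7 days, offset 0–3, 5% missed) from 1.6 to between 1.4 and 1.0. End-of-treatment assessments can also break a long gap, and some responders are censored earlier for new anticancer therapy. If, for illustration, half of events had an end-of-treatment assessment in the gap and 20% of responder events were already censored for new therapy, that case falls from 1.54 (a separate run) to about 0.8. The documents give neither rate, but both act downward.

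The damage can also be seen. SAP Table 6 lists this reason separately from new therapy, a by-subject listing is planned, and sensitivity analysis 1 restores every affected event.

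All of this stands as a limit on magnitude. It does not make the rule correct. A listing that has to be checked against visit dates does not repair the primary p-value, and sensitivity analysis 1 also restores events after new therapy, so it cannot isolate this error. The no-miss case needs no modelling: a death on day 520 after a clean Week 53 assessment is censored before Week 77 is due.

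**Conclusion.** The concern holds. The four limits are arithmetically sound but tied to the wrong date, so the primary analysis can censor responders who missed one visit or none, contrary to the SAP's stated purpose.

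The day ranges follow from the schedule and the SAP's own limits, and need only nominal visit dates with no intervening unscheduled or end-of-treatment assessment. The frequency rests on the assumed attendance, visit timing and event dating above, and the caveats push it down. The expected effect on the test and on power is small, with no established direction. What remains is a risk to a borderline result and inaccurate censoring reasons. It is worth correcting, though it does not threaten the trial's validity.

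**What to change.** Amend SAP 7.7.1.1.1 before unblinding, in one of two ways.

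1. **Count visits.** Count the scheduled visits whose full ±7-day window opens after the last adequate assessment and closes before the event, and censor only if two or more were missed. Add that a scheduled visit held outside its window counts as attended. Otherwise a W77 visit held 9 days early on day 524, followed by a missed W101 and an event on day 709, would score two misses when only one occurred.
2. **Keep the limits but key them to the last adequate assessment.** W25 or earlier, more than 119 days; W33, more than 147; W41, more than 259; W53 or later, more than 343. On nominal dates this gives no wrong flags and leaves no closed double miss uncensored. Of the 225 within-window timing pairs, it flags none with no visit missed and 28 with one missed. In simulation 0 to 0.3 events per trial remain wrongly censored with half-and-half dating, and up to 0.6 if all events are visit-dated.

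The second option handles an unscheduled last assessment less well. With a last assessment on day 400 and W77 and W101 missed, both windows close by day 708, but the rule flags only from day 400 + 344 = 744.

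Either way, state whether visit weeks run from randomization or C1D1. Also state that the same definition governs the missed-assessment censoring of DOCR, DOCRh, DOR and DOCRi in SAP Table 8, which gives no day limits. The cost is SAP wording and a small programming change; no further data are needed.

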7.7.1.2. Sensitivity Analyses for EFS

The following sensitivity analyses will be performed:

1. EFS will be tested using the log-rank test stratified by the IRT randomization stratification factors and based on the FAS. The time of relapse or death is determined using the actual date of relapse or death, even in situations where relapse or death is observed after two or more missing disease assessment or start of subsequent anticancer therapy.
2. EFS will be tested using the unstratified log-rank test and based on the FAS.
3. EFS will be tested using the log-rank test stratified by the IRT randomization stratification factors and based on the PPS.
4. EFS will be tested using the log-rank test stratified by the randomization stratification factors derived based on data provided by the Investigator in the eCRF and based on the FAS.
5. EFS will be tested using the log-rank test stratified by the IRT randomization stratification factors and based on the FAS. For the subjects who do not achieve CR by Week 24, instead of being considered to have had an EFS event at Day 1 of randomization, the event time will be either 24 weeks or EOT, whichever is earlier.

